#### ***Shipment samples***

The shipment of samples to the reference laboratories in Cotonou and Kigali will be organized, based on parallel sputum aliquots in validated sputum preservative, to avoid contamination, for phenotypic testing if not completed on-site; as IATA Category A shipment), and for Deeplex testing. Quality control and troubleshooting will be provided by shipping samples to ITM, where the same Deeplex tests will be set-up, as well as to Genoscreen, which will offer support to all three laboratories using the test.

Sample shipping has been reinforced through organizing a 2-day IATA shipping course in Cotonou, followed by an examination for IATA certification for all partners.

#### ***DataToCare***

To help increase the GeneXpert connectivity, we will assess the landscape and their eventual existing connectivity solutions in all countries at the start of the project. This will allow us to develop a plan for implementation and upgrade of connectivity solutions in selected sites adapted to the local context. In the selected sites, we will provide ongoing support after installation, and monitor the Xpert results, diagnostic delay, and users' satisfaction.

## **9. Data Analysis**

For the phase I and II of the study 1 (validation of Deeplex against phenotypic DST & validation of InSilixa and Xpert 2nd generation against Deeplex results), we will validate the molecular assays for their performance (Se and Sp) on the diagnosis of RIF resistance, against phenotypic DST on solid medium as gold standard, with resolution of discordances by classic target sequencing of the *rpoB* gene. Similar analyses will be conducted to determine the performance for the diagnosis of isoniazid and fluoroquinolone resistance.

An interim analysis will be performed after 350 RR-TB patients have been recruited in order to test our assumptions regarding resistance proportions and consider adjustment of sample size or recruitment strategy.

For the study 2, the results will be analyzed with time dependent Cox regression to identify the optimal time point to identify patients who are at risk of failing treatment.

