#### **Technical background – Deeplex assay**

The Deeplex test, developed by Genoscreen (8), consists of a targeted Next Generation Sequencing (NGS) assay, coupling multiplex PCR to deep sequencing. This approach is designed to be directly applicable on clinical samples, providing species- and *M. tuberculosis* lineage identification, and detection of drug resistance. The Deeplex test can simultaneously detect mutations in numerous genes that confer resistance to multiple anti-TB drug classes: The amplicons are deep sequenced on a MiniSeq platform, This molecular assay is coupled to a dedicated secured, cloud-based bioinformatics application, including analysis of deep sequencing data and final reporting of identification of resistance associated mutations. The MiniSeq based Deeplex test however requires specific infrastructure, equipment and technical skills and will only be deployed in well-established reference laboratories such as Laboratoire de Référence des Mycobactéries (LRM, Cotonou), Rwanda Biomedical Center (RBC, Kigali), and ITM in Antwerp. A sample referral system will be set up between the different countries to ensure shipment to the two African laboratories; ITM will serve as a back-up and external referent. Once concurrent phenotypic assays will not be needed any longer in the context of this project, sputum referral systems can include inactivation, such as in ethanol, to facilitate sample shipment (non-infectious, and no cold chain required).. The Deeplex assay will in a second phase also serve for validation of the point of care tests,

as it will detect all mutations in the respective genes. Moreover, it may identify novel mutations, including those unique to strains circulating in Sub-Saharan Africa.

**Table 1.** Antibiotics, and their gene targets, to which resistance is detected in Deeplex

Gene target	Antibiotic	Deeplex
aphC	Isoniazid	+
eis	kanamycin	+
embB	ethambutol	+
ethA	ethionamide	+
fabG1	isoniazid	+
gidB	streptomycin	+
gyrA	Fluoroquinolones*	+
gyrB	Fluoroquinolones*	+
inhA	isoniazid	+
katG	isoniazid	+
pncA	pyrazinamide	+
rplC	linezolid	+
rpoB	rifampicin	+
rpsL	streptomycin	+
rrl	linezolid	+
rrs	Injectable agents	+
tlyA	capreomycin	+

\*including ofloxacin, levofloxacin, moxifloxacin and gatifloxacin

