### 1. Study design:

Two multi center observational studies will be conducted:

- *Study 1:* Cross sectional study for TB cases aged  $\geq 15$  (all RIF resistant (RR) ones (new cases or retreatment patients) and equal number of RIF sensitive retreatment

patients from the same country) with comparison of TB resistance diagnostic test performance at baseline. There are 2 phases in this project; phase 1 is the comparison of Deeplex results against the phenotypic results (Gold standard), phase 2 is the comparison of Insilixa and Xpert 2nd generation results against Deeplex (gold standard).

- *Study 2:* Cohort study of RR-TB patients (recruited in Study 1) under treatment with comparison of the performance of FDA or Xpert compared to solid culture

The study flow chart is placed in annex 1 of this protocol

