## **4. Sample size**

The partners in the proposal expect to recruit at least 80% of the eligible retreatment patients (those with RIF resistance -considered as MDR- and equal numbers of RIF sensitive patients) presenting for diagnosis and care. Based on previous years data, over 4700 patients at risk of RR TB are on average collectively being screened annually out of which 590 (15%) are diagnosed as being RR-TB (Table 2, in Background).

For the validation of the novel tests (Study 1), we will recruit all RR patients and equal numbers of RIF susceptible patients, for a total of 1420 RR- and 1420 RIF susceptible patients. In the table below, we summarize the power we expect to have to detect resistance to the key drugs:

**Table 3.** Sample size considerations against **phenotypic** gold standard (Phase 1), and the **genotypic** gold standard (Phase 2, see study flow chart in Annex 1), with each phase including 1420 patients, half of whom will have RR TB, for a total of 2840 patients.

Drug	Expected prevalence of resistance in RIF R (n=710 each phase)	Expected total prevalence of resistance (n=1420 each phase)	Expected sensitivity and precision against phenotypic test	Expected specificity and precision against phenotypic test	Expected sensitivity and precision against genotypic test	Expected specificity and precision against genotypic test
RIF	710 (100%)	710 (50%)	98% +/- 1%	98% +/-1%	98% +/- 1%	98% +/-1%
INH	675 (95%)	923 (65%)	90% +/- 1%	98% +/-1%	98 +/- 1%	98% +/-1%
FQ	43 (6%)	43 (3%)	85% +/- 8%	98% +/-1%	98%, range 88%-100%	98% +/-1%

RIF= rifampicin, INH=isoniazid, FQ=fluoroquinolones

The estimated prevalence of resistance is based on the WHO report (1) and personal communications. This sample size will be ample to validate these tests for resistance to RIF, isoniazid, and fluoroquinolones, according to established guidelines (9).

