## 6. Data management & Data Collection

### **Data collected:**

For each patient enrolled in study 1 & 2, an expanded laboratory request form will be completed.

For all patients the following data will be collected:

- Baseline characteristics (mostly those collected from routine monitoring, including demographic- and contact information, detailed treatment history including details such as failure vs relapse prior MDR treatment, return after loss to follow-up), risk factors for (resistant) TB
- Phenotypic drug sensitivity tests (phase I of Study 1 only)
- Deeplex results (phase I and II of the Study 1)
- Programmatic treatment outcomes

In addition:

- for the phase 2 of the study 1 (validation of InSilixa and 2nd line Xpert test) the results of these 2 tests (InSilixa and 2nd line Xpert) will also be recorded
- for all patients enrolled as RR, the following additional information will be recorded:
  - monthly FDA results,
  - monthly GeneXpert and culture results,
  - treatment outcomes

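### The plan does not say whether rpoB sequencing of discordant RIF results changes the 2x2 table (if it does, sensitivity and specificity cannot fall), and it names the phase 2 reference inconsistently

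*Combined protocol and SAP*

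**What the plan says.** Methods, section 9 (Data Analysis) covers both phases in one sentence, which opens "For the phase I and II of the study 1". Its parenthesis describes phase 1 as Deeplex against phenotypic DST and phase 2 as InSilixa and the second-line Xpert against Deeplex. Its main clause then sets RIF Se and Sp "against phenotypic DST on solid medium as gold standard", "with resolution of discordances by classic target sequencing of the" *rpoB* gene. Similar analyses are announced for isoniazid (INH) and fluoroquinolones (FQ), with no gene named.

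Other places bear on this:

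- Methods, section 1 (Study design): "phase 1 is the comparison of Deeplex results against the phenotypic results (Gold standard", and for phase 2 "generation results against Deeplex (gold standard".
- Methods, section 4, Table 3 sizes phase 1 under columns such as "Expected sensitivity and precision against phenotypic test". Its caption gives phase 2 a genotypic gold standard.
- The Synopsis also compares the two phase 2 tests with Deeplex.
- Methods, section 6 (Data collected) lists "Phenotypic drug sensitivity tests (phase I of Study 1 only").
- Table 1 of the Introduction ("Antibiotics, and their gene targets, to which resistance is detected in Deeplex") includes *rpoB* as the rifampicin target.

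The plan does not say whether resolution changes the table, which figure is primary, whether unresolved figures will be reported, or whether any concordant samples will be sequenced.

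**The concern.** The resolution clause is attached to the calculation of Se and Sp, so an analyst could reasonably take it to mean that the reference result of a discordant patient is replaced by the sequencing result. Under that reading only patients who count against the index test are re-examined. They can leave an error cell but never enter one. The estimate can therefore move only in the test's favour, and it is no longer the comparison with phenotype that the design defines and Table 3 sizes.

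In phase 1 the resolver is also not independent of the index test, because both read *rpoB*.

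In phase 2 the two candidate references give different sets of discordant pairs. An analyst who follows the main clause would look for phenotypic results that the data list assigns to phase 1 only.

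The Rationale section expects the developers to use the validation results in regulatory and WHO submissions. The choice between resolved and unresolved figures should therefore not be left until the data are seen.

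**Working it through.** **Inputs.** From Table 3, per phase: 710 RIF-resistant and 710 RIF-susceptible patients, with expected Se and Sp of 98% +/- 1% each. The confidence level is not stated, so I assume 95% two-sided. The share r of discordant results that sequencing overturns in favour of the index test is not in the documents, so I show the range 0 to 1.

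**The plan's own precision.** Wald half-width = 1.96 × sqrt(0.98 × 0.02 / 710) = 0.0103, or 1.03 points. This agrees with the stated +/-1%.

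**Direction.** Suppose x false positives (FP) are moved to true positives (TP) and y false negatives (FN) to true negatives (TN):

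- Se = (TP + x) / (TP + x + FN − y)
- Sp = (TN + y) / (TN + y + FP − x)

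Both are non-decreasing in x and in y, whatever the quality of the resolver. As a check in whole patients (TP 696, FN 14, FP 14, TN 696), all 15 × 15 = 225 combinations of x and y were enumerated. None lowers Se or Sp, and one (x = y = 0) leaves both unchanged.

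This depends on sequencing discordants only. If concordant results were sequenced too, the figures could fall. For example, with half of each discordant cell overturned and an assumed 10 errors found in each concordant cell, Se = Sp = (696 + 7 − 10) / 710 = 97.6%.

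**Size in phase 1.** Expected cells are TP = TN = 0.98 × 710 = 695.8 and FN = FP = 14.2, so 28.4 patients are discordant. With the same share r in both error cells, 14.2r patients leave each row and 14.2r enter it. The row totals stay at 710, and Se = Sp = (695.8 + 14.2r) / 710 = 0.98 + 0.02r.

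| r | Se = Sp | Shift (points) |
|---|---|---|
| 0 | 98.0% | 0 |
| 0.1 | 98.2% | 0.2 |
| 0.25 | 98.5% | 0.5 |
| 0.5 | 99.0% | 1.0 |
| 0.75 | 99.5% | 1.5 |
| 1 | 100% | 2.0 |

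The shift matches the planned half-width at r = 1.03 / 2 = 0.51.

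With unequal shares, each mainly moves its own measure. If half of the FN and none of the FP are overturned, Se = 695.8 / 702.9 = 98.99% and Sp = 702.9 / 717.1 = 98.02%.

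**Why the resolved figure cannot be read alone.** Assume that concordant results are correct.

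- Case A: DST is always right and the resolver is a coin flip. True accuracy is 98/98 and the resolved figure is 99/99, 1 point too high.
- Case B: half of the discordants are DST errors and the resolver is perfect. True accuracy is 99/99, the resolved figure is 99/99, and the unresolved 98/98 is 1 point too low.

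Both cases give the same unresolved table and the same resolved figure. Sequencing discordants alone cannot tell them apart.

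**Phase 2 reference.** Four statements point to Deeplex or a genotypic standard: the Synopsis, the Study design section, the Table 3 caption, and the parenthesis in Data Analysis. One statement, the main clause in Data Analysis, names phenotypic DST for both phases. The data list restricts phenotypic DST to phase 1. Section 8 says that first-line DST is routine at all sites, so some phenotypic results may exist in phase 2, but they are not listed as study data for that phase.

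**The case against.** **Resolution may be only explanatory.** The plan never says that cells are changed. If sequencing merely accounts for discordances, there is no shift. This stands, so a reader who infers that the RIF figures will be inflated goes further than the documents. The point is conditional, and the omission is what needs repair.

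**The overturn share has no source.** This stands. A reader might infer a bias larger than the planned precision, but that needs r above about 0.51. At r of 0.1 to 0.25 the shift is 0.2 to 0.5 points. The shared *rpoB* target is a reason to expect sequencing to side with Deeplex, but the documents do not say how often.

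**Phenotypic DST is itself fallible.** The Synopsis says that few laboratories can perform it correctly, so case B is a live possibility and an unresolved primary figure may be too low. This is a good reason to show both figures. It does not remove the one-way movement of discordant-only resolution.

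**Phase 2 is defined.** A reader might infer that phase 2 has no reference standard. The documents do not support that, because Deeplex or a genotypic standard is given in four places. What stands is a contradiction with one clause.

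**The arithmetic might seem to carry over to phase 2,** since Table 3 repeats the RIF inputs there. It does not carry over safely. The Introduction's background on the second-line Xpert describes a cartridge for second-line drugs, used in patients already found RIF-resistant, so a 710/710 RIF table does not follow for that test. In phase 2 the resolver also shares its gene with the Deeplex reference. I claim no phase 2 magnitude.

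**Conclusion.** The concern holds in conditional form. If resolution means reclassifying discordant results, phase 1 RIF Se and Sp cannot fall. At Table 3 inputs they rise by 2r points, about 1 point at r = 0.5, which is roughly the whole planned +/-1%. If sequencing only explains discordances, the shift is zero. The size rests on the 710/710 split and 98%/98% of Table 3, on equal overturn shares in the two error cells, and on an r that the documents do not give. The direction rests only on discordant-only sequencing, which is what the plan describes.

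Separately, the phase 2 reference is stated inconsistently, so which pairs are discordant in that phase is unclear. No size is given for phase 2, INH or FQ. This should be settled before the analysis, but it does not threaten the design.

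**What to change.** In Data Analysis:

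1. State that the primary Se and Sp are the unresolved figures against the named reference, which is phenotypic DST in phase 1.
2. Report target sequencing of discordants in a separate descriptive table that leaves the 2x2 cells unchanged. Label any resolved figure secondary and print it beside the unresolved one.
3. Correct the main clause so that phase 2 uses the Deeplex reference stated elsewhere, in line with the restriction of phenotypic DST to phase 1 in the data list.
4. Say whether the similar analyses for INH and FQ include resolution. If so, name the genes and apply the same rule.
5. Record the sequencing result as its own item in the data list.

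The cost is wording and one data item, and the sequencing itself is unchanged. The downside is that the primary figure may be too low where phenotypic DST is wrong (1 point in case B), and showing both figures makes that visible. Sequencing a weighted random sample of concordant pairs would say more. It would cost more and, for Deeplex, would still rely on the gene that Deeplex reads, so I do not ask for it.

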## **2. Rationale**

We anticipate that the impact of the DIAMA project, if the results are as promising as expected, will be potentially paradigm-shifting. We foresee that MDR-TB will move from an often terminal illness with grave prognosis to a readily recognizable and treatable disease, in which treatment success can be predicted early, so treatment can be modified in 'real' time. The novel tests that identify specific resistance to particular drugs used for the treatment of resistant TB allow for a way of 'personalized medicine', and by monitoring the impact of specific mutations on the outcome of MDR treatment, we anticipate learning which mutations should lead to treatment modifications in order to enhance the chance of treatment success. In addition, we will learn whether heteroresistance, which is the simultaneous occurrence of bacterial populations with and without resistance, is of clinical relevance. Lastly, the fact that the Deeplex assay gives full sequence information on a large number of genes allows us to detect, for the first time, whether different mutations are common in circulating drug resistant strains in the participating countries in Sub-Saharan Africa. Such results will thus not only inform the treatment algorithms used in clinical trials for MDR-TB, yet also provide fundamental insights into the pathogenesis underlying the development of TB resistance.

Once the validation of the novel diagnostic tests for TB resistance mutations will be completed in the DIAMA proposal, the companies that have developed these tests will

include these results in their respective applications for approval by regulatory authorities, and for endorsement by WHO. The monitoring of MDR patients on treatment with FDA microscopy is readily implementable in most peripheral microscopy centers.

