## **3. Study population**

In order to be eligible for study 1 and 2, study participants **must meet the following criteria:**

- Being  $\geq 15$  year old
- Having a positive test on GeneXpert (*M. tuberculosis*) with or without resistance detected to rifampicin
- Willing and able to provide written informed consent, or for minors: assent from these patients and consent from a legal representative

In addition, for the study 2 (cohort study), only patients for whom RIF resistance was detected with GeneXpert at baseline and who started MDR-TB treatment will be eligible.

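### Study 2 picks its best monitoring time point from the data with no planned correction for that selection, so performance reported at the chosen month and test would be optimistic

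*Combined protocol and SAP*

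**What the plan says.** Methods 9 (Data Analysis) gives Study 2 one sentence: "time dependent Cox regression to identify the optimal time point to identify patients who are at risk of failing treatment".

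The candidates come from Methods 6 (Data collected), which lists "monthly FDA results" and "monthly GeneXpert and culture results" for every patient enrolled as RR. Study Objectives 2 adds that Xpert is to be followed through Ct values, so a Ct cut-off may also be searched. Methods 1 (Study design) makes performance an output: "Cohort study of RR-TB patients (recruited in Study 1) under treatment with comparison of the performance of FDA or Xpert compared to solid culture". Culture-free monitoring is a primary objective.

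The Study 2 population is restricted in Methods 3: "only patients for whom RIF resistance was detected with GeneXpert at baseline and who started MDR-TB treatment will be eligible". Methods 4 (Sample size) plans two phases, "with each phase including 1420 patients, half of whom will have RR TB, for a total of 2840 patients". Methods 1 defines those phases for the Study 1 test comparisons only. Study 2 has no sample size, expected failure rate or precision target.

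On mutations, Secondary objectives 1 and 2 relate additional resistance, and specific INH and PZA mutations, to programmatic outcome. The Rationale states the intended use: "we anticipate learning which mutations should lead to treatment modifications in order to enhance the chance of treatment success". The Background also foresees adding validated mutations to the InSilixa assay. Methods 9 gives no analysis, error rate or list of mutations for this work.

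**The concern.** Picking the best of several months and tests by their observed performance favours candidates that were lucky in this sample. The winner's observed performance is then, on average, higher than it would be in new patients. This holds for any data-driven rule, so defining the optimal time point more precisely would not remove it. Only estimation that allows for the selection, or fresh patients, does.

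Failures are likely to be the scarce group, so most of the error falls on sensitivity. That is the figure a programme would look at before replacing monthly culture with one FDA or Xpert reading. If it is several points too high, more failing patients would be missed than the report suggests.

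The mutation work has a related weakness. Several mutations may be tested against outcome with no control of chance findings, and the Rationale wants the results to inform treatment.

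**Working it through.** **1. The plan's own figures.** The counts agree: 1420/2 = 710 RR per phase, 2 x 710 = 1420 RR, and 2 x 1420 = 2840 in total. The RIF precision also reproduces: 1.96 x sqrt(0.98 x 0.02/710) = 1.0 point. There is no Study 2 figure to reproduce. Because Study 2 takes only RR patients who started treatment, 1420 is a ceiling.

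**2. Assumed inputs (none is in the documents).** The earliest failure outcome is at month 6, so months 1-5 with two tests give 5 x 2 = 10 candidates. Failure is taken as 5% or 10%, that is 0.05 x 1420 = 71 or 0.10 x 1420 = 142 failures. Within-patient correlation is 0.5. Results are binary, and the candidate with the highest Youden index (sensitivity + specificity - 1) wins. Optimism is the winner's observed Youden index minus its true value, averaged over simulated cohorts. Ranges cover repeat runs.

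| True pattern over months | 10% failure | 5% failure |
|---|---|---|
| Equal (Se 60%, Sp 85%) | 5.4 points | 7.1-7.2 points |
| Mild gradient (Se 50-60%, Sp 80-85%) | 3.1-3.8 | 5.4-5.8 |
| Clear gradient (Se 40-65%, Sp 70-88%) | 1.8-2.3 | 2.8-3.8 |

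That is about 2-7 points.

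**3. Sensitivity to the assumptions.** A second set-up uses one test, Sp 85% and correlation 0.3-0.8, again picking by Youden index. It measures optimism in sensitivity alone, at N = 1420. Equal months use 6 or 9 candidates; the other two patterns use 6.

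| Failure rate (failures) | Equal months, Se 70% | Se 50, 58, 65, 70, 72, 70% | One clearly best month, Se 30 rising to 85% |
|---|---|---|---|
| 3% (43) | 5.1-8.9 | 4.0-5.7 | under 1 |
| 5% (71) | 4.1-6.7 | 3.0-4.4 | about 0 |
| 10% (142) | 2.6-4.8 | 1.6-2.9 | about 0 |
| 15% (213) | 2.4-3.9 | 1.6-2.1 | about 0 |

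With N = 710 and equal months the figures are 4.4-7.4 points at 10% failure and 6.0-10.3 at 5%. Over all settings the range is about 0-9 points at N = 1420 and 0-13 at N = 710.

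**4. Cost of confirming by phase.** For a sensitivity of 60% at 10% failure, the 95% half-width with all 142 failures is 1.96 x sqrt(0.6 x 0.4/142) = 8.1 points. With the 71 failures of one phase it is 1.96 x sqrt(0.6 x 0.4/71) = 11.4 points.

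Follow-up is also shorter in Phase 2. Expected recruitment is 0.80 x 590 = 472 RR per year, so 1420/472 = 3.0 years. From a start in the first quarter of 2017, recruitment ends around the first quarter of 2020. With the study ending on 31 May 2021, the last patients have roughly 14 months.

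**5. Mutations.** With K independent null tests at 5%, the expected number of chance findings is 0.05K and the chance of at least one is 1 - 0.95^K.

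- K = 5 (the isoniazid and pyrazinamide gene targets in Table 1): 0.25 expected; 1 - 0.95^5 = 23%.
- K = 17 (all gene targets in Table 1): 0.85 expected; 1 - 0.95^17 = 58%.

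The number to be tested is not stated, so these are illustrations. Requiring p < 0.05 in both phases has a price. By Schoenfeld's formula, with 20% carriage, a hazard ratio of 2 and 10% failure, power is 65% per phase, hence 0.65 x 0.65 = 42% for both. A single pooled test with Bonferroni adjustment for 17 has 63%.

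**The case against.** The strongest reply is that the plan is silent here and does not commit an error. It does not say that accuracy will be quoted at the chosen month, that the Youden index will be used, or that mutations will be tested at an unadjusted 5%. The comparison with solid culture could mean month-by-month agreement, which involves no selection. Time-dependent Cox regression on Ct values also differs from ranking binary tests, so the simulation describes a procedure that the plan does not spell out.

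Much of this stands. A reader might infer that the plan intends to pick and report in the same patients and to call chance mutations real. The documents do not say so; they only fail to prevent it. A reader might also take 2-7 points as a property of this study, but every input behind it is assumed.

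It is tempting to say that two ready-made RR cohorts of 710 exist for validation. The phases belong to Study 1, 710 is an upper limit for Study 2, and Phase 2 would have the shorter relapse follow-up.

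Finally, one might multiply 5% by the 117 mutations on the InSilixa panel. That is a panel size, not a list of outcome tests. Secondary objective 2 concerns specific INH and PZA mutations, and the Background lets mutations reach the chip through phenotypic validation too.

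One part of the reply fails. A plan that announces a data-driven choice, names performance as an output and has no correction step will, followed as written, give an optimistic figure for the winner. The direction does not depend on the simulation settings; only the size does.

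**Conclusion.** The concern holds in a conditional form. Performance reported at the month and test that Study 2 selects would be optimistic, because nothing in Methods 9 corrects for the selection. With 5-10% failure, 10 candidates, correlation 0.5 and up to 1420 RR patients, the optimism could be about 2-7 Youden points, nearly all in sensitivity. It is close to 0 if one month is clearly best, and exceeds 7 with few failures or fewer patients starting treatment. The documents cannot narrow this, since they give no failure rate, number of candidate months or correlation.

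The missing multiplicity control for mutations is a real but secondary gap. It rests on the Background, Rationale and Secondary objectives rather than on the time-point sentence. The documents do not support a count of false mutations, because the number tested is not stated and some tested mutations may have real effects.

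The point is worth settling before the Study 2 data are analysed, because the remedy costs little.

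**What to change.** Add to Methods 9:

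- **Time point.** Analyse all Study 2 patients. State the candidate months, tests and any Ct cut-offs, and the criterion that picks the winner. Repeat the whole selection inside each bootstrap sample, and report optimism-corrected sensitivity and specificity beside the uncorrected values. This takes SAP wording and modest programming, with no new patients, visits or samples, and no loss of events. When candidates are nearly tied the bootstrap may remove most rather than all of the optimism, so also report how often each candidate is selected.
- **Optional check.** Choose in the Phase 1 RR patients and confirm in the Phase 2 RR patients. This removes the selection effect from the confirmed estimate. It costs precision (about +/-11 instead of +/-8 points on a sensitivity of 60% at 10% failure) and leaves shorter relapse follow-up in Phase 2. The text would have to extend the phases to Study 2.
- **Mutations.** List the mutations to be tested against outcome. Apply a 5% Benjamini-Hochberg false discovery rate across all of them in the pooled cohort before calling any outcome-linked. The cost is some power against unadjusted tests; pooling avoids the larger loss that requiring significance in both phases would bring in the example above.
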